Systane Hydration PF is a recently released preservative-free artificial tear that is able to supplement the ocular surface's moisture while simultaneously soothing the eye. Systane Hydration PF has HydroBoost technology, which is thought to enhance the drop's effectiveness by incorporating ingredients that increase drop retention. While Systane Hydration PF should in theory improve the symptoms and subsequently the quality of life of patients who have DES, this clinical application has yet to be tested. This drop furthermore is available in both unit-dose and multi-dose options; however, it is unclear if patient perceive a difference between the two dispensing methods. Therefore, the primary purpose of this study is to recruit patients who have DES and to treat them with Systane Hydration PF and determine how regular use of this drop impacts a patient's ocular surface symptoms and overall quality of life. This study will secondarily compare the two dispensing methods to determine if patients prefer one method over the other.

II. SPECIFIC AIM

Aim: Determine the effect of Systane Hydration PF on dry eye symptoms and visual quality of life in subjects who have Digital Eye Strain (DES).

Hypothesis 1: Systane Hydration PF will significantly improve IDEEL Work scores in heavy digital device users (≥ 8 hours of wear/day).

Hypothesis 2: Subjects will report higher ease of use satisfaction when using multi-dose Systane Hydration PF compared to unit-dose Systane Hydration PF.

III. STUDY DESIGN

Subjects

This two-week, three-visit study will be conducted at the University of Alabama at Birmingham (Birmingham, AL, USA). A total of 30 subjects will be recruited since this is a descriptive study. Subjects will be recruited from each site via clinic records, email, and fliers. Adult (>18 years) patients who answer yes to the following two questions and use digital devices (e.g., computers, tablets, or smart phones) ≥ 8 hours/day will be recruited:

"Are your eyes dry, irritated, or itchy or do they burn while using a digital screen, like a computer or smartphone? Yes or No

“Eye fatigue is the physical discomfort of your eyes after spending periods of time throughout the day in front of a digital screen, like a computer or smartphone.”⁴ Do you have eye fatigue based upon the this definition? Yes or No

Subjects will also be required to have a Work Impact of Dry Eye on Daily Life (IDEEL) score ≤ 80 to ensure that they have clinically meaningful symptoms,⁵ and they will be required to have an Ocular Surface Disease Index (OSDI) score between 13 and 32 (inclusive) to ensure that they have mild to moderate dry eye symptoms.^{6,7} Subjects will be excluded if they had worn contact lenses in the past week or during the course of the study, have known systemic health conditions that are thought to alter tear film physiology (e.g., Sjögren's syndrome), have a history of ocular surgery within the past 12 months, have a history of severe ocular trauma, active ocular infection or inflammation, are currently using isotretinoin-derivatives or ocular medications, are currently using a dry eye treatment other than artificial tears, are currently using more than 4 drops of artificial tears per day in each eye, or if they are pregnant or breast feeding.⁸ If subjects are currently using artificial tears, they will be required to refrain from using them for at least 24 hours before their baseline visit, and they will only be allowed to use Systane Hydration during the study.

Surveys and Clinical Tests

This will be a prospective, investigator-masked clinical trial, which will be registered with ClinicalTrials.gov. Subjects who meet all study criteria will be enrolled into the study. The contents of the drops will be concealed from the subjects. Clinical measurement will be obtained from both eyes of each subject and testing will be performed in the below order. Testing order was designed to sequentially administered the least invasive to most invasive test. This methodology will ensure that a previous procedure will have a minimal effect on all subsequent assessments.⁹ Subject will be asked to bring their spectacles to the study visit and to adhere to the contact lens exclusion factors described above throughout the study.

Visit 1

1. Subject History, Eligibility, Informed Consent: Subjects will be asked to complete a screening survey at the first study visit to verify that they are eligible for the study. All relevant ocular, systemic, and surgical history will be gathered via a questionnaire developed by the investigators. This questionnaire will also ask about digital device usage and eye comfort while using digital devices. The subjects will complete the OSDI questionnaire, and they will be required to have a score between 13 and 32 (inclusive). The subject will be asked to complete the Work IDEEL, and they will be required to have a score ≤ 80 . Non-eligible subjects will be dismissed at this time or rescheduled depending upon the reason for ineligibility. Eligible subjects will be enrolled, consented, and requested to sign a privacy document.

2. Impact of Dry Eye on Daily Life (IDEEL) questionnaire: The full Impact on Daily Life segment of the IDEEL questionnaire will be self-administered electronically to understand how quality of life and common daily activities are affected by eye comfort (e.g., computer work, near work).¹⁰

3. Visual Acuity: The subject's visual acuity will be measured with a Bailey-Lovie high-contrast (logMAR) chart or equivalent. If the patient is unable to read the 20/40 letters (0.3 logMAR), the investigator will pinhole over the patient's unaided or presenting refractive error correction to determine the subject's visual potential.

4. Slit-Lamp Biomicroscopy: The investigator will use a slit-lamp biomicroscope to document normal and/or remarkable findings of the anterior eye structures: eyelashes (blepharitis), eyelids, conjunctiva, and cornea. Eyelids will be graded based upon a grading scale that was developed by the investigators.

5. Subject Randomization: The examiner will use an electronic randomization system to place the subject in the Systane Hydration Multi-Dose group or the Systane Hydration Unit-Dose group. Subjects will be required to use their allocated drop two to four times per day in each eye.

6. Subject Compliance: Subjects will be given a daily log to record the time and number of drops used each day; these data will be used to determine drop compliance for each dispensing method. They will also be asked to record the duration and type of digital device use each day.

Visit 2

1. Testing: Subjects will be asked to repeat the IDEEL and clinical tests described above at this visit. The compliance log will likewise be collected at this visit and a new one will be given.

2. Drop Application Satisfaction Survey: An investigator developed survey will be created based upon the glaucoma literature to understand patient satisfaction related to applying Systane Hydration via the Unit-Dose and Multi-Dose options.

3. Subject Crossover: Subjects will be switched to the opposite treatment group. No washout period will be needed because all subjects will be using Systane Hydration; they will just be applying the drop via the alternative dispensing method for the second week of the study. Subjects will be required to use their allocated drop two to four times per day in each eye.

Visit 3

1. Testing: Subjects will be asked to repeat the IDEEL and clinical tests described above at this visit. The compliance log will likewise be collected at this visit.

2. Drop Application Satisfaction Survey: An investigator developed survey will be created based upon the glaucoma literature to understand patient satisfaction related to applying Systane Hydration via the Unit-Dose and Multi-Dose options.

3. Study Completion: The examiner will reveal the study details to the subjects (Systane Hydration PF). The subject will be compensated for their time, and they will be released from the study at this time.

Data Management & Analysis

Surveys and all data will be collected via a secured web service (REDCap) at the time of the study visit. [name], MS, PhD, Professor and Vice Chairman in the Department of Epidemiology at the University of Alabama at Birmingham, will perform the statistical analyses. All data will be analyzed with SAS Version 9.4 (SAS; Cary, NC, USA). ANOVA, T-tests, and chi-square tests will be used when comparing variables. If the assumptions of these tests cannot be met suitable alternative statistical tests (e.g., Wilcoxon Rank Sum Test, Fisher's Exact Test) will be used instead. The questionnaire data will furthermore be presented in a table that will describe the frequency by which each subject indicated each questionnaire response.

Training of Study Personnel

Prior to enrolling any subjects all clinical examiners will participate in a meeting run by [name]. This full investigator meeting will ensure that all study investigators are performing the procedures in the same manner.

Data from each investigator's first subject will also be monitored for quality control before sites are allowed to enroll additional subjects.

IV. Study Timeline

	2021	2021	2021	2021	2021
	Mar	Apr	May	Jun	Jul
Activity					
Contracting					
IRB Preparation					
Data Collection					
Data Analysis					
Final Study Report					

V. Publication Plans

An abstract evaluating the effects of Systane Hydration PF on ocular comfort and quality of life will be submitted to the Global Specialty Lens Symposium 2022. A summary of this work will be submitted as a manuscript to *Contact Lens & Anterior Eye*.

VI. Conclusions

This project will provide some of the first data related to the quality of life of patients who have DES who are heavy digital device users. It will likewise provide insights into the usefulness of Systane Hydration PF in patients who have DES, and it will provide some of the first guidance related to dosing methods of dry eye treatments. Ultimately, after completion of this study, clinicians will have a better understanding of the symptomatology surrounding DES and how Systane Hydration PF affects these symptoms.

VII. References

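### The primary purpose, Aim and Hypothesis 1 claim an effect of the drop, but every subject uses the drop in both weeks, so the study can show only an uncontrolled change from Visit 1.

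*Combined protocol and SAP*

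**What the plan says.** The introduction gives the primary purpose as to recruit patients with digital eye strain, "treat them with Systane Hydration PF and determine how regular use of this drop impacts" their symptoms and quality of life. Section II (Specific Aim) repeats this as "Determine the effect of Systane Hydration PF on dry eye symptoms and visual quality of life", and Hypothesis 1 makes it specific: "Systane Hydration PF will significantly improve IDEEL Work scores in heavy digital device users". Hypothesis 2 concerns satisfaction with the two dispensers.

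Section III (Study Design) sets out the following:

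- **Sample size (Subjects).** "A total of 30 subjects will be recruited since this is a descriptive study".
- **Entry.** "Subjects will also be required to have a Work Impact of Dry Eye on Daily Life (IDEEL) score ≤ 80", with an OSDI score from 13 to 32 inclusive. Both are completed at Visit 1. Previous artificial tears are stopped at least 24 hours beforehand.
- **Visit 1.** Item 1 takes the eligibility score: "The subject will be asked to complete the Work IDEEL, and they will be required to have a score" of 80 or less. Item 2 then says "The full Impact on Daily Life segment of the IDEEL questionnaire will be self-administered electronically". Item 5 randomises between the multi-dose and unit-dose presentations of the same drop.
- **Visits 2 and 3.** The IDEEL is repeated at each. At Visit 2 subjects change dispenser without washout, on the ground that everyone remains on the same drop.
- **Masking.** "The contents of the drops will be concealed from the subjects".
- **Data Management & Analysis.** ANOVA, t-tests and chi-square tests are listed, with non-parametric or exact alternatives. None is tied to Hypothesis 1, and no baseline score or follow-up visit is named for it.

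**The concern.** The primary purpose, the Aim and Hypothesis 1 are all statements about what the drop does. The design contains no group, and no period after Visit 1, in which a subject is without the drop. A significant rise in the Work score would be read as support for Hypothesis 1, yet an inert drop could produce one through expectation of benefit or the passage of time. Entry is also decided at the only pre-treatment visit, partly on the endpoint score itself, so the reference value is a selected one. At stake is the main conclusion: the study would report as an effect something that it can only observe as a change.

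**Working it through.** **Which contrast each hypothesis has**

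| | Week 1 | Week 2 | Contrast available |
|---|---|---|---|
| Sequence A | drop, multi-dose | drop, unit-dose | dispenser |
| Sequence B | drop, unit-dose | drop, multi-dose | dispenser |
| Drop absent | none | none | none after Visit 1 |

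Hypothesis 2 has a randomised, within-subject contrast. Hypothesis 1 has only Visit 2 or Visit 3 against Visit 1. The observed mean change is the sum of the drop's effect, placebo response, change over time (including any effect of stopping previous tears before Visit 1) and bias from selection at entry. One before-after difference cannot separate these. This step needs no assumed number.

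**The plan's own figure.** The only design figure is 30 subjects. No significance level, power, effect size or SD accompanies it, so it cannot be reproduced.

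**Can the selection bias be sized?** The documents give no mean, SD or reliability for IDEEL or OSDI, so every input here is an assumption. A Work cut of 80 or below is meant to secure meaningful symptoms, so a higher Work score is better. The OSDI window is meant to secure mild to moderate symptoms, so a higher OSDI is worse.

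Assume normal scores, an inert drop, no placebo response, the qualifying score as baseline, and visit-to-visit correlation r.

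*Work cut alone:* expected change = (1 − r) × SD × φ(z)/Φ(z), with z = (80 − mean)/SD.

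- Mean 60, SD 15, r 0.8: z = 1.333; 0.2 × 15 × 0.1640/0.9088 = +0.5
- Mean 60, SD 20, r 0.7: z = 1; 0.3 × 20 × 0.2420/0.8413 = +1.7
- Mean 70, SD 20, r 0.8: z = 0.5; 0.2 × 20 × 0.3521/0.6915 = +2.0
- Mean 80, SD 20, r 0.7: z = 0; 0.3 × 20 × 0.3989/0.5 = +4.8

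*Work cut and OSDI window together:* assume also OSDI SD 15, a same-visit correlation with Work of −0.6, and a cross-visit correlation of −0.6 × r. OSDI then adds nothing to the prediction of the later Work score once the first Work score is known, so expected change = (1 − r) × (candidate mean − mean Work score of those admitted). The admitted mean comes from numerical integration over both criteria. Each cell gives the admitted mean, then the expected change.

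| Work mean / SD / r | OSDI mean 25 | OSDI mean 35 | OSDI mean 45 |
|---|---|---|---|
| 60 / 15 / 0.8 | 59.6; +0.1 | 63.4; −0.7 | 66.5; −1.3 |
| 60 / 20 / 0.7 | 57.6; +0.7 | 61.8; −0.5 | 65.2; −1.6 |
| 70 / 20 / 0.8 | 63.3; +1.3 | 66.4; +0.7 | 68.8; +0.2 |
| 80 / 20 / 0.7 | 67.4; +3.8 | 69.6; +3.1 | 71.3; +2.6 |

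For example, 0.3 × (60 − 65.2) = −1.6. The ceiling of 32 removes candidates with the worst symptoms, who tend to have low Work scores, and so works against the Work cut. The floor of 13 works with the cut. In every setting tried the window lowered the expected change, and at a candidate Work mean of 60 it reversed the sign in four of six cells.

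If Visit 1 item 2 re-asks the Work items and serves as baseline, (1 − r) becomes (same-visit correlation − r). That shrinks the bias in either direction but does not remove it while same-day scores correlate more closely than scores from different visits.

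**The case against.** The best defence is that the study calls itself descriptive, is small and short, and names no comparator in Hypothesis 1, so a before-after test can be run and the lack of a control is plain to any reader. Part of this stands: the paired test is feasible, and change during use is a legitimate thing to report. But the descriptive label is used only to justify 30 subjects. It does not limit a hypothesis that the drop will significantly improve a score, nor an Aim to determine its effect. Masking does not help either: both dispensers hold the same drop, so concealing its contents supplies no comparator and leaves expectation in place.

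A second defence concerns selection. A reader might infer that admitting subjects on a low Work score makes a spurious significant rise likely, and might put a percentage on it. The documents do not support that. Such percentages follow only if the OSDI window is ignored and a candidate distribution is invented. With the window included, the expected change may be close to zero or negative. This objection stands in full against any claim about the size or direction of regression to the mean. It leaves placebo response and time untouched.

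It is also fair to say that Visit 1 item 2 is the natural baseline, since it calls for the full segment and gives computer work as an example. The plan does not say so, however. That gap, and the effect wording in the Publication Plans and Conclusions, are secondary to the main point.

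**Conclusion.** The concern holds. As designed, randomisation informs only Hypothesis 2, and Hypothesis 1 can be tested only as an uncontrolled change from Visit 1. A positive result would not show that the drop caused the change. This rests on the documents' own description of the groups, the crossover and the visits, and on no assumed figure.

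Selection at entry is a further possible source of bias, of unknown size and unknown direction. The range of −1.6 to +4.8 points covers only the settings tried, under assumed inputs. It shows that the sign is not settled and is not an estimate for this trial.

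Two stronger readings should be avoided. One is that the plan has a known, inflated false-positive rate; the documents give nothing from which to compute it. The other is that the study cannot be run or analysed without a control arm; it can, provided that the claim is limited to change during use.

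**What to change.** 1. Restate Hypothesis 1 as: *IDEEL Work scores will improve from Visit 1 during use of Systane Hydration PF.* Test and report it as the mean paired change with a 95% CI.
2. Before data are seen, name the Visit 1 score that serves as baseline (the eligibility score, or item 2 if it re-asks the Work items) and one follow-up visit, Visit 2 or Visit 3.
3. Word the primary purpose and the Aim as change during use, and carry that wording into the report.
4. State that the design cannot attribute the change to the drop, because nothing controls for placebo response, time or selection at entry.

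The cost is wording only: no new subject, visit or questionnaire. The downside is a weaker claim for Hypothesis 1. Hypothesis 2 and its randomised comparison are unaffected.

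### Known allergy or intolerance to the study drop is not an exclusion, and subjects are not told the contents until Visit 3

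*Combined protocol and SAP*

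**What the plan says.** The exclusion list is in III. Study Design, under Subjects. It opens with contact lenses: "Subjects will be excluded if they had worn contact lenses in the past week or during the course of the study". It goes on to systemic conditions that affect the tear film, recent eye surgery, severe trauma, and active infection or inflammation. The medication items are worded by current use: "are currently using isotretinoin-derivatives or ocular medications, are currently using a dry eye treatment other than artificial tears". The list closes with "are currently using more than 4 drops of artificial tears per day in each eye, or if they are pregnant or breast feeding". People already using artificial tears may enrol if they stay under the frequency cap and stop for a day before baseline. During the study, "they will only be allowed to use Systane Hydration during the study".

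Under Surveys and Clinical Tests the protocol states: "The contents of the drops will be concealed from the subjects". Disclosure is placed at Visit 3, item 3: "The examiner will reveal the study details to the subjects (Systane Hydration PF".

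At Visit 1, item 1 collects relevant eye, general-health and surgical history on an investigator-developed questionnaire, and item 5 randomises the subject. The dosing instruction is given at Visit 1, item 5 and again at the Visit 2 crossover: "Subjects will be required to use their allocated drop two to four times per day in each eye".

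**The concern.** If the product were named at the outset, a subject who had reacted to it before could recognise it and decline. Concealing the contents weakens that safeguard, and an eligibility criterion would normally take its place. Here none does. The crossover gives no relief, because both periods use the same drop.

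What is at stake is a foreseeable and avoidable exposure of a subject with a known earlier reaction. No statistical quantity depends on it.

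**Working it through.** The plan gives no figure to reproduce, so the check is a reading of the eligibility and visit text, plus one piece of exposure arithmetic.

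**1. Could any listed exclusion capture a past reaction to the drop?**
- Contact lenses, surgery, trauma, pregnancy and breast feeding: no.
- Systemic conditions: these are limited to conditions thought to affect tear film physiology. Intolerance to an ingredient is not such a condition.
- Active infection or inflammation: this would catch a reaction present on the day, not one that has resolved.
- Medication and dry eye treatment items: these turn on current use. A person who reacted to a drop has probably stopped using it and so passes.
- Artificial tear frequency: this caps current use and does not ask about tolerance.

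No item applies.

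**2. Could Visit 1 screening capture it?** The item 1 history could elicit a past reaction. The protocol does not name drop reactions as something to ask about, and it links no answer on them to ineligibility. Subjects who satisfy the listed criteria are enrolled.

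**3. When does the subject learn what the drop is?** According to the visible text, at Visit 3, item 3, after both treatment weeks.

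**4. Does either period avoid the product?** No. Visit 2, item 3 justifies the absence of a washout by the fact that everyone uses the same drop throughout.

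**5. Planned exposure.** The inputs are the study length ("This two-week, three-visit study will be conducted at the University of Alabama at Birmingham", so 14 days), 2 to 4 applications daily per eye, and 2 eyes.
- Lower end: 2 × 2 × 14 = 56 applications.
- Upper end: 4 × 2 × 14 = 112 applications.

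These totals apply to a subject who completes both weeks at the stated frequency. A subject who reacts may stop sooner.

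**The case against.** The strongest reply is that the omission is small and partly covered. A subject can report a past reaction at Visit 1 without knowing what the study drop is. The protocol names a single product for both groups, so the site can match the report to it. Consent also takes place at Visit 1, and the consent pages, which were not available for review, may carry an ingredient or allergy warning. The product is described as recently released, which makes earlier exposure to it less likely. The clinical tests are repeated at Visit 2, before the second week.

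Much of this stands. It rules out saying that the subject has no way to raise a past reaction or could not recognise the product. It does not close the gap: reporting depends on an unprompted answer, no listed criterion acts on it, and a consent warning would not alter the list that the site applies.

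A reader might infer four stronger things that the documents do not support:
- *The rule allowing only Systane Hydration contradicts the concealment.* It does not have to. The rule can be given to subjects as an instruction to use only the supplied drop, and the visit instructions speak of the allocated drop.
- *Concealing the product serves neither hypothesis.* Hypothesis 1 concerns a self-reported score with every subject on the same drop and no untreated control. Hiding the brand can limit brand expectation there.
- *A reacting subject would bias the results.* Worsening caused by the drop is part of the effect that Hypothesis 1 asks about. For Hypothesis 2, a reaction present in both weeks falls on both dispensers within the same subject and does not clearly favour either.
- *The chance of enrolling such a subject can be stated.* The documents give neither a rate of intolerance nor the share of the 30 subjects who use artificial tears. Any probability would only restate the assumed rate.

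**Conclusion.** The concern holds as a gap in eligibility. The visible exclusion list has no item for known allergy or intolerance to the study drop or its ingredients, and the contents are concealed until Visit 3. The history questionnaire neither names drop reactions nor links them to a criterion. A person with a known earlier reaction is therefore eligible and is assigned the product in both periods, with 56 to 112 planned applications if the study is completed.

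The ground is subject safety alone. How often this would happen cannot be judged from the documents, and no sample size, test or estimate changes. The conclusion rests on the exclusion list as written. It makes no claim about what the consent form says.

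**What to change.** Add known allergy or intolerance to the study drop or any of its ingredients to the exclusions under Subjects. Add a matching question to the history questionnaire at Visit 1, item 1, so that it is answered before randomisation at item 5. One way to keep the brand hidden is to ask against an ingredient list that does not name it. If the consent form already carries a warning, its wording should agree with the new criterion.

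The cost is one eligibility line and one screening question. An ingredient list slightly weakens the concealment of the product, which has some value for Hypothesis 1. It has no effect on the dispenser comparison, because both groups receive the same drop and the question reveals nothing about allocation.

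### The aim covers dry eye symptoms, but the OSDI, which the plan uses to grade them at entry, is not scheduled after Visit 1

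*Combined protocol and SAP*

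**What the plan says.** The introductory text gives the primary purpose as to "determine how regular use of this drop impacts a patient's ocular surface symptoms and overall quality of life". Section II sets one aim: "Determine the effect of Systane Hydration PF on dry eye symptoms and visual quality of life in subjects" with digital eye strain. Both pair symptoms with quality of life. Section V plans an abstract on ocular comfort and quality of life, and section VI expects clinicians to learn how the drop affects symptoms.

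Section III, Subjects, sets two questionnaire criteria for entry and ties both to symptoms:

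- OSDI: "score between 13 and 32 (inclusive) to ensure that they have mild to moderate dry eye symptoms".
- Work IDEEL: "score ≤ 80 to ensure that they have clinically meaningful symptoms".

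Visit 1 item 1 (history, eligibility, consent) contains the OSDI and the investigators' history questionnaire, of which the plan says: "This questionnaire will also ask about digital device usage and eye comfort while using digital devices". Visit 1 item 2 is the Impact on Daily Life segment of the IDEEL, described as showing the effect of eye comfort on quality of life and everyday tasks. Visual acuity and slit-lamp examination follow.

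Item 1 at both Visit 2 and Visit 3 reads: "Subjects will be asked to repeat the IDEEL and clinical tests described above at this visit". Neither visit mentions the OSDI or the history questionnaire.

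**The concern.** The scale that the plan uses to establish the level of dry eye symptoms has a baseline value and no follow-up value. Any statement about symptom change must then be read from a score that the plan presents as a measure of impact on daily life. The IDEEL items are not reproduced in the documents, so a reader cannot check how far that score reflects symptoms themselves. One instrument is left to stand for both halves of the aim without a stated basis.

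The omission is permanent once the visits have passed, because questionnaire responses not collected at Visits 2 and 3 cannot be recovered. What is at stake is the symptom part of the aim, the planned abstract's reference to ocular comfort, and the symptom statement in the conclusions.

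**Working it through.** There is no stated figure to reproduce. The check lists every instrument in the introductory text and section III against the three visits.

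| Instrument | What the plan uses it for | Visit 1 | Visit 2 | Visit 3 |
|---|---|---|---|---|
| Two yes/no questions on digital eye strain | Recruitment | Recruitment only | No | No |
| OSDI | Grading dry eye symptoms at entry | Yes | No | No |
| Eye-comfort items in the history questionnaire | History | Yes | No | No |
| IDEEL, Impact on Daily Life (including Work) | Entry (Work) and outcome | Yes | Yes | Yes |
| Visual acuity, slit lamp | Function and signs | Yes | Yes | Yes |
| Daily log | Drop use and device use | Issued | Collected, reissued | Collected |
| Satisfaction survey | Ease of applying the drop | No | Yes | Yes |

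The log and the satisfaction survey contain no described symptom entry, and acuity and slit lamp are not symptom measures. One symptom-related instrument remains with a baseline and a follow-up value: the IDEEL daily-life segment.

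**Could the OSDI be among the clinical tests that are repeated?** The text points the other way. The subsection heading lists surveys separately from clinical tests. The OSDI is called a questionnaire and sits in the eligibility step. The follow-up instruction names one questionnaire to repeat, and it is the IDEEL.

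**Counts.** The only input is the planned sample size: "A total of 30 subjects will be recruited since this is a descriptive study". The counts are maxima that assume all 30 complete.

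- Subject-visits: 30 × 3 = 90.
- OSDI forms scheduled: 30 × 1 = 30 of 90. IDEEL forms scheduled: 30 × 3 = 90 of 90.
- Possible paired changes from Visit 1: 30 × 2 = 60. OSDI: 30 × 0 = 0 of 60. IDEEL: 30 × 2 = 60 of 60.

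The 60 changes are two per subject and are not independent; each follow-up visit offers 30 pairs.

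**Effect on the hypotheses.** Hypothesis 1 concerns IDEEL Work, which is measured at all three visits. Hypothesis 2 concerns ease-of-use satisfaction, which is surveyed at Visits 2 and 3. Hypotheses blocked: 0 of 2.

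**The case against.** The strongest reply is that the plan already has a repeated symptom measure. It describes a Work IDEEL score of 80 or below as marking clinically meaningful symptoms, Hypothesis 1 names IDEEL Work as the effect measure under the single aim, and that score is collected at every visit. On this view the sponsor has chosen how to operationalise the aim, and using the OSDI only for eligibility is a legitimate choice in a study labelled descriptive. What is left would be a mismatch of wording that can be cured at no cost.

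Much of this is fair. Symptoms are not wholly unmeasured, and the documents reproduce the items of neither scale, so they cannot show that the OSDI is the better symptom measure. The counts above restate one fact, namely that the OSDI is given at one visit of three, and show nothing about bias or precision. A before-after OSDI change would also have no untreated or placebo comparison and would be open to regression to the mean. The same weakness applies to IDEEL Work, which is likewise selected at entry.

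The point survives because the plan names symptoms and quality of life as two things, grades dry eye symptoms with the OSDI, and describes the repeated IDEEL segment in terms of daily-life impact. A descriptive study should be able to describe what its aim names, or its aim should be narrowed to match.

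**Conclusion.** The concern holds, and the plan should be changed. As scheduled, no change from baseline can be reported for the OSDI or for eye comfort during device use: 0 of 60 possible OSDI changes against 60 of 60 for the IDEEL. The limit falls on the symptom part of the aim and the matching statements in the purpose, publication plan and conclusions. It does not touch either hypothesis.

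This rests on reading the Visit 2 and Visit 3 testing instruction as written. If the sponsor meant the OSDI to be repeated, the schedule still needs to say so, because examiners will follow the written list. The finding on the schedule is firm. How much symptom information would be lost depends on the content of the IDEEL segment, which the documents do not give.

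**What to change.** Add the OSDI by name to item 1 (Testing) at Visits 2 and 3. Report the mean paired change from Visit 1 to each of these visits with a 95% confidence interval. Label it a descriptive, uncontrolled before-after change that is open to regression to the mean because entry is restricted to OSDI 13 to 32. Attach the same caution to IDEEL Work, which is selected at 80 or below.

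If the eye-comfort items are repeated too, report them as response frequencies. Data Management & Analysis already plans this for questionnaire data, and no score is described for these items.

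If no scale is added, restrict the symptom wording in the purpose, aim and conclusions, and the reference to ocular comfort in the publication plan, to what the IDEEL daily-life scores measure.

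The first option costs at most 30 × 2 = 60 extra OSDI forms, a few minutes each, at existing visits and in the data system already in use. It needs no new visits, staff or procedures, and the downside is slightly more burden on subjects. The wording option costs nothing.
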